3.2 Study Endpoints

Baseline data will be obtained at time of presentation including eligibility criteria, medical history, and current influenza symptoms.

Symptoms will be recorded using the scoring system described in a meta-analysis of "all published and unpublished Roche-sponsored randomized placebo-controlled, double-blind trials of oseltamivir treatment in adult influenza" (⁹). "The primary outcome will be time to alleviation of all symptoms. Seven influenza symptoms (nasal congestion, sore throat, cough, aches and pains, fatigue, headaches, and chills or sweats)" will be graded by severity as "absent" (0), "mild" (1), "moderate" (2), or "severe" (3). Alleviation will be defined to arise when all symptoms scored as absent or mild, and remain so for at least 21.5 hours." The secondary endpoints will be the time to alleviation and to complete resolution of individual and all symptoms. Patients will be followed daily until all symptoms have completely resolved and fever has remained less than 100° F for 24 hours, or for a maximum of 21 days if symptoms have not yet completely resolved for 24 hours.

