7 STATISTICAL PLAN

7.1 Sample Size Determination

Duration of influenza was chosen as our primary outcome because previous studies described beneficial effects of elderberry extract on this outcome (1-4) and published data is available on the elderberry extract manufactured by the company supplying elderberry extract for our study to use to calculate our sample size.(3) Forty-six total influenza positive patients randomized at a 1:1 ratio with 23 active and 23 placebo patients are needed for a power of 90% to detect a mean difference in duration of illness of at least two days with a Type I error rate of 0.05, assuming standard deviations of 1.3 and 2.5 days in the supplement and placebo groups respectively.(3) Sixty-five to one hundred patients will be enrolled in our study. We are assuming a cautious estimate of nearly a 30% dropout rate.

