7.2 Statistical Methods

Study groups will be compared on duration of illness using a two-sample unequal variance t-test; the data will be transformed (such as by log-transformation) to meet distributional assumptions, and the mean

difference between groups with 95% confidence interval will be reported. Secondary analyses will assess the time to resolution of individual symptoms, and compare study groups on adherence to protocol and side effects using two-sample t-tests and Chi-square tests as appropriate. These analyses will be performed on an intent-to-treat basis. All tests will be two-tailed and performed at a significance level of 0.05. SAS 9.4 software will be used for all analyses.

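### Section 7.2 tests everything at 0.05 with no ordering or exploratory label, and its secondary list does not match 3.2; for the seven secondary efficacy tests it names, the chance of a false positive is about 18–30%

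*Combined protocol and SAP*

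**What the plan says.** Section 3.2 names one primary endpoint: "The primary outcome will be time to alleviation of all symptoms". It grades seven symptoms and then states: "The secondary endpoints will be the time to alleviation and to complete resolution of individual and all symptoms".

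Section 7.2 gives the primary analysis ("Study groups will be compared on duration of illness using a two-sample unequal variance t-test") and then the rest: "Secondary analyses will assess the time to resolution of individual symptoms, and compare study groups on adherence to protocol and side effects", by t-tests and chi-square tests as appropriate. The error rule covers all of these alike: "All tests will be two-tailed and performed at a significance level of 0.05".

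Section 7.1 powers only the comparison of illness duration. The text contains no multiplicity adjustment, no testing sequence and no label separating confirmatory from exploratory results.

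**The concern.** There are two linked gaps.

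First, each secondary test has the same 0.05 threshold as the primary, and nothing says what may be concluded if a secondary result is significant when the primary is not. The objective in section 2 concerns duration and severity of symptoms in general and does not tie a positive conclusion to the primary. A single-symptom p-value below 0.05 could therefore be presented as a significant effect.

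Second, the lists in 3.2 and 7.2 differ, so the number of secondary tests is not fixed in advance. Followed literally, 7.2 leaves complete resolution of all symptoms without a named test. Yet follow-up runs until that event or day 21 (3.2, 5.5), and the daily questionnaire in 14.2 has a date-and-time field for it. Meanwhile each single-symptom resolution time is tested at a full 0.05.

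**Working it through.** **The plan's own figure.** The documents state no family-wise error rate. The figure that can be checked is the sample size for the single primary comparison (7.1): difference 2 days, SDs 1.3 and 2.5, two-sided 0.05, 90% power, 23 per arm.

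- Standard error at 23 per arm = √((1.3² + 2.5²)/23) = √(7.94/23) = 0.588, so the noncentrality is 2/0.588 = 3.40, with about 33.1 Welch degrees of freedom.
- Power from the noncentral t is 91.0% at 23 per arm and 89.7% at 22. So 23 is the smallest number reaching 90%, and the stated 46 reproduces.
- Dropout: 46/(1 − 0.29) = 64.8, rounded up to 65, which agrees with the lower enrolment figure and a dropout of nearly 30%.

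This calculation gives the whole 0.05 to one comparison. That is sound for the primary and says nothing about the secondaries.

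**Counting the secondary efficacy tests.**

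- Section 3.2: 2 event types × (7 symptoms + all symptoms) = 16. Removing the primary (alleviation of all symptoms) leaves 15.
- Section 7.2: 7 individual resolution times.
- In 3.2 but not in 7.2: 7 individual alleviation times + 1 complete resolution of all symptoms = 8; and 15 − 7 = 8.

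**Chance of at least one p<0.05 when the supplement has no effect.** For k independent tests it is 1 − 0.95^k:

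- k = 7: 1 − 0.95^7 = 0.302
- k = 15: 1 − 0.95^15 = 0.537

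For k test statistics with common correlation ρ, with G standard normal:

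P = 1 − E[{Φ((1.96 − √ρ·G)/√(1−ρ)) − Φ((−1.96 − √ρ·G)/√(1−ρ))}^k]

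For false results favouring the supplement only, drop the second Φ term. Under independence this gives 1 − 0.975^k, so 1 − 0.975^7 = 0.162. The documents give no correlations, so the values of ρ are assumptions.

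| Assumed ρ | 7 tests, either direction | 7 tests, favouring supplement | 15 tests, either direction | 15 tests, favouring supplement |
|---|---|---|---|---|
| 0 | 30.2% | 16.2% | 53.7% | 31.6% |
| 0.5 | 23.0% | 11.5% | 36.1% | 18.1% |
| 0.7 | 17.8% | 8.9% | 25.7% | 12.8% |
| 0.9 | 11.4% | 5.7% | 14.4% | 7.2% |

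The expected number of false positives does not depend on ρ: 7 × 0.05 = 0.35, or 15 × 0.05 = 0.75.

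**Given a non-significant primary.** Simulating with the primary equally correlated with the secondaries, the chance of any p<0.05 among the seven named tests is about 21% at ρ = 0.5 and 15% at ρ = 0.7. In favour of the supplement it is about 10% and 7%.

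**After the fix.** With complete resolution of all symptoms tested only after a significant primary, a false significance claim under no effect requires the primary to be falsely significant first. The chance of any such claim across the two tests is therefore at most 5%.

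**The case against.** The best defence is that the essential hierarchy is already there. Section 3.2 names one primary, 7.1 powers only illness duration, and 7.2 calls the remaining analyses secondary. Unadjusted secondary tests in a Phase IV trial of 65 to 100 patients are common and are often left to careful reporting. Much of this stands, and it is why the point is a cheap improvement and not a threat to the trial's main conclusion.

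Several stronger readings are tempting but not supported:

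- A reader might take 26–54% as the risk under 7.2. It is not: that range needs all 15 times of 3.2 to be tested, and 7.2 names seven. An endpoint with no test adds no false positives.
- A reader might treat 54% as realistic. Independence is ruled out by the definitions. A symptom cannot be completely resolved before it is alleviated, and the all-symptom times depend on the individual ones. Nor is 26% a floor, as the figure at ρ = 0.9 shows.
- A reader might infer that a null primary makes a significant symptom result likely. For the seven named tests, at correlations of 0.5 to 0.7, the chance is 15–21%, about half of it in favour of the supplement.
- A reader might infer that the plan treats any secondary p<0.05 as proof of efficacy, or that section 1.1 presents this trial as the more rigorous test. Neither is stated. Section 1.1 criticises earlier studies for size, lack of intent-to-treat analysis and place of publication, and does not mention multiplicity.
- A reader might add the side-effect items to the count. Section 7.2 does not say that each is tested separately, and safety comparisons look for harm and do not support efficacy claims.

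It could also be argued that duration of illness in 7.2 means complete resolution, so that endpoint does have a test. The primary in 3.2 would then have none. On either reading, one all-symptom time lacks a named analysis.

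**Conclusion.** The concern holds as a modest one. Section 7.2 applies 0.05 to every test without an order or an exploratory label, and its secondary list omits eight of the 15 secondary times in 3.2, including complete resolution of all symptoms. With no true effect, the seven efficacy tests that 7.2 does name carry roughly an 18–30% chance of at least one significant result, and 9–16% of one favouring the supplement. Extending the tests to all of 3.2 without a rule would raise the risk further.

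These figures rest on an assumed common correlation between 0 and 0.7 and on normal test statistics. The primary comparison's 5% error and its power are not affected. The mismatch between the two lists does not depend on any correlation.

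**What to change.** Revise 7.2 in three steps:

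1. Make its secondary list match 3.2, and state that duration of illness means the primary endpoint defined there.
2. Replace the blanket significance rule with a fixed order. Test time to alleviation of all symptoms at two-sided 0.05; only if that is significant, test time to complete resolution of all symptoms at two-sided 0.05.
3. Report the 14 individual-symptom times and adherence as exploratory estimates with 95% confidence intervals and no significance claims. Report side effects descriptively as safety data.

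The cost is a short protocol amendment, which under section 11 goes to the IRB. Sample size, data collection and primary power do not change. The price is that an isolated single-symptom p-value below 0.05 can no longer be called significant, and complete resolution cannot be claimed if the primary fails.

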7.3 Subject Population(s) for Analysis

All-randomized population: Any subject randomized into the study, regardless of whether they received study drug

8 SAFETY AND ADVERSE EVENTS

8.1 Definitions As Defined by Cleveland Clinic IRB-60 Adverse Event Reporting

The Institutional Review Board requires Investigators to monitor and report Adverse Events. The Institutional Review Board is responsible to assess changes in risk to ensure safety protections of human subjects.

An **Unanticipated Problem Involving Risks to Participants or Others** is any event that (1) is unforeseen, (2) caused harm or placed a person at increased risk of harm, and (3) is related to the research procedures.

An Adverse Event (AE) is any untoward or unfavorable medical occurrence, including any abnormal sign (for example, abnormal physical exam or laboratory finding), symptoms, or disease. Adverse events can encompass both physical and psychological harms.

An **Internal Adverse Event** (AE) is an untoward medical occurrence, which occurs to participants in research conducted by Cleveland Clinic and/or Cleveland Clinic is the IRB of record.

A Serious Adverse Event (SAE) is any adverse experience that results in any of the following outcomes:

- o death
- a life-threatening experience
- o inpatient hospitalization or prolongation of existing hospitalization
- o a persistent or significant disability/incapacity
- a congenital anomaly/birth defect
- Important medical events that may not result in death, be life-threatening, or require hospitalization may be considered a serious adverse drug experience when, based upon appropriate medical judgment, they may jeopardize the patient or subject and may require medical or surgical intervention to prevent one of the outcomes listed in this definition.

An **Unexpected Adverse Event** means any AE not previously known or included in the current Investigator's Brochure, consent form or other risk information.

Related/Possibly Related means there must be reasonable evidence to suggest the event was caused by the drug, device or investigational intervention.

8.2 Recording of Adverse Events

At each daily contact, using questionnaires in Appendix 1,the investigator will seek information on adverse events detailing any Grade 1 through 4 DAIDS side effects as defined in Section 14.1, pages 24-25. Patients will be instructed to contact the study personnel at [contact] for all suspected Grade 3 or 4 side effects (First calling 911 for Grade 4 side effects and contacting study personnel once able) Patients will then be triaged as appropriate to their primary medical provider or urgent or emergency care facilities. Information on all adverse events will be recorded immediately in the source document, and also in the appropriate adverse event section of the case report form (CRF). All clearly related signs, symptoms, and abnormal diagnostic procedures results will also be recorded in the source document.

The clinical course of each event will be followed until resolution, stabilization, or until it has been determined that the study treatment or participation is not the cause. Serious adverse events that are still ongoing at the end of the study period will be followed up to determine the final outcome. Any serious adverse event that occurs after the study period and is considered to be possibly related to the study treatment or study participation will be recorded and reported immediately.

8.3 Reporting of Serious Adverse Events

A serious adverse event will be reported to the study investigator/sponsor by telephone within 24 hours of the event. A Serious Adverse Event (SAE) form must be completed by the investigator and faxed to the study sponsor, [name] within 24 hours. The investigator will keep a copy of this SAE form on file at the study site. Report serious adverse events by phone and facsimile to: [name] [contact], [contact] respectively.

At the time of the initial report, the following information will be provided:

- Study Identifier
- Study Center
- Subject Number
- A description of the event
- Date of onset
- Current Status
- Whether study supplement was discontinued
- Reason why the event is classified as serious
- Investigator assessment of the association between the event and study treatment

Significant new information on ongoing serious adverse events will be provided promptly to the study sponsor.

8.3.1 IRB Notification by Investigator

Reports of all serious adverse events (including follow-up information) will be submitted to the CCF IRB per the guidelines located in the CCF IRB Standard Operating Procedures under IRB-60 in manual. Copies of each report and documentation of IRB notification and response will be filed in the regulatory binder.

The following four types of events will be reported to the Cleveland Clinic IRB:

- 1. Adverse events which are serious, unexpected, and related or possibly related to participation in the research.
- 2. Serious adverse events that are expected in some subjects, but are determined to be occurring at a significantly higher frequency or severity than expected.
- 3. Other unexpected adverse events, regardless of severity, that may alter IRB analysis of the risk versus potential benefit of the research and, as a result, warrant consideration of substantive changes in the research protocol or informed consent process/document.
- 4. Unanticipated Problems involving risks to subjects or others or any serious or continuing noncompliance with this policy or the requirements or determinations of the IRB."

8.3.2 FDA Notification by Sponsor (if applicable)

The study investigator/sponsor shall notify the FDA by telephone or by facsimile transmission of any unexpected fatal or life-threatening experience associated with the use of the supplement as soon as possible but no later than 7 calendar days from the sponsor's original receipt of the information.

If a previous adverse event that was not initially deemed reportable is later found to fit the criteria for reporting, the study sponsor will submit the adverse event in a written report to the FDA as soon as possible, but no later than 15 calendar days from the time the determination is made.

8.4 Unblinding Procedures

The safety of the subject always comes first, we will seriously consider if unblinding the study therapy is necessary to ensure a subject's safety. If unblinding study supplement on a subject is deemed necessary, the study biostatistician will unblind the subject and documentation of this in the subject's source document will be completed. In most cases, the unblinding will be part of managing an SAE, and will be reported with the SAE, however, in cases where unblinding was not associated with an SAE, such actions should be reported in a timely manner. We will use the same timeline requirements for investigator reporting of SAEs, (notification of sponsor within 24 hours by phone or fax, followed by a written narrative of the event within 48 hours.)

8.5 Stopping Rules

Stopping rules will not be used in this study.

8.6 Medical Monitoring

The Principal Investigator and Monitor will oversee the safety of the study at his/her site. This safety monitoring will include careful assessment and appropriate reporting of adverse events as noted above, as well as the construction and implementation of a site data and safety-monitoring plan (see section 9 Auditing, Monitoring and Inspecting). Medical monitoring will include a regular assessment of the number and type of serious adverse events.

8.7 Criteria for Withdrawal of Patient from Study.

Patients may choose to withdraw from the study at any time.

Patients with DAIDS Grade 4 symptoms, felt to be due to a study medication side effect by their physician of record, will be withdrawn from the study with ongoing follow-up of symptoms until the patient's acute symptoms resolve.

If patients become too ill to tolerate oral study medication they will be withdrawn from the study with ongoing follow-up of symptoms until the patient's acute symptoms resolve.

If patients develop an allergy to study medication or become pregnant during the study they will be withdrawn from the study with ongoing follow-up until their acute symptoms resolve.

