6 STUDY PROCEDURES

6.1 Pre-registration and Screening

If patients are eligible and interested in participating we will review the informed consent with them, and their families if necessary, and obtain written informed consent or assent, depending upon patients' ages.

6.2 Visit 1

Visit 1 will be completed at the same visit for registration and screening. A nasopharyngeal swab will be obtained for Roche^R cobas^R Liat^R PCR assays for influenza A&B prior to enrollment in study to confirm all study patients have documented influenza.

Informed consent, and assent when indicated, will be obtained prior to completing any study related assessments. Eligibility for the study will be confirmed and baseline data will be obtained.

All women of childbearing potential will have a urine pregnancy test before starting and upon completion of the study. Pregnancy tests will be done following standard Cleveland Clinic operating procedures and documented in the electronic medical record, the case report forms and REDCap Cloud. The result of the pregnancy test(s) will be disclosed to the minor subject and their parent(s)/legal guardian.

Patients will be instructed on how to return unused study medication in the provided stamped envelope addressed to the study coordinator, and for women of childbearing potential how to obtain an end of study pregnancy test at the most convenient Cleveland Clinic laboratory.

Patients will be given their randomly assigned study medication and instructed to give 15 ml of medication, in a measuring cup provided, 4 times a day for 5 days for ages 13 and above and 15 ml 2 times a day for ages 5-12 for 5 days. They will be given their first dose of study medication prior to leaving the emergency room.

Patients will be asked to please avoid taking any additional cold or influenza medications if possible. They will be told they may take ibuprofen or acetaminophen for pain or fever. They will be asked to report daily all medications taken not reported on their day 1 visit. Taking additional medications will not disqualify patients from the study other than taking prescription antibiotics or antivirals prior to the start of the study.

Patients will receive daily phone calls to remind them to take each dose of their study medication and to answer their daily surveys (see Appendix 1). All patients who do not answer their daily surveys on the first call, will receive two additional phone call attempts to have the survey answered.

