6.3 Visit 2, etc.

After the initial in-person study visit at the time of enrollment, all subsequent visits will be by telephone. As previously outlined, women of childbearing potential will have an end of study urine pregnancy test to be arranged at a nearby Cleveland Clinic Laboratory.

Study Assessments

Procedure	Screening/Baseline Visit One	Daily Phone Call Until Well	Final Study Visit
Confirm Inclusion/Exclusion Criteria	Х		
Obtain Informed Consent	Х		
Nasopharyngeal swab for PCR test for influenza A&B, RSV	Х		
Urine Pregnancy Test for Women of Childbearing Potential	Х		Х
Screening/Enrollment Questionnaire	Х		
Dispense Study Medication	Х		
Daily (Symptom) Questionnaire	Х	Х	Х
Record Side Effects/AE/SAE		Х	
Study Drug Return			Х

Laboratory Procedures

Roche^R cobas^R Liat^R PCR assays for influenza A&B and RSV on day of entry into study. This is CLIA waived testing.

Urine pregnancy testing initially will be done using a point of care pregnancy test per standard Cleveland Clinic procedures. The end of study pregnancy testing will be done per usual protocol at Cleveland Clinic outpatient laboratories.

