Grade 2 Moderate is defined as "Symptoms causing greater than minimal interference with usual social and functional activity".

Grade 3 Severe is defined as "Symptoms causing inability to perform usual social and functional activity".

Grade 4 Potentially Life-Threatening is defined as "Symptoms causing inability to perform basic self-care functions OR medical of operative intervention indicated to prevent permanent impairment, persistent disability or death".

The patients will be asked to call immediately to call the study personnel mobile phone at [contact] for any suspected side effects at Grades 3. These patients will be referred by the principal investigator to their primary care physician, or urgent or emergency care facilities as appropriate with follow-up of their acute symptoms by the principal investigator or study coordinators until these symptoms resolve.

PATIENTS WILL BE TOLD TO CALL 911 FOR ALL GRADE 4 SYMPTOMS. After their health care needs are met for Grade 4 symptoms we will ask that they please call study line for follow-up and study personnel will also keep in touch with them daily until they are well.

ON LAST DAY OF STUDY CONFIRM ALL SYMPTOMS RESOLVED AND TEMPERATURE (<100⁰F) FOR 24 HOURS AND ALSO RECORD:

BEST GUESS OF EXACTLY WHEN ALL SYMPTOMS AND FEVER HAD BEEN RESOLVED FOR 24 HOURS TIME ____AM/PM __DATE ____ GUESS WHETHER STUDY MEDICATION WAS ELDERBERRY ____OR PLACEBO _____ WAS YOUR GUESS BASED *MOSTLY* BECAUSE OF: YOUR RESPONSE TO TREATMENT ____ TASTE OF MEDICATION ____ OR SPECIFY SOMETHING ELSE

NUMBER OF BOTTLES OF STUDY MEDICATION REMAINING TO NEAREST ¼ _____ NUMBER OF BOTTLES TO NEAREST ¼ OR TABLETS OF OSELTAMIVIR (TAMIFLU^R) OR BALOXAVIR MARBOXIL (XOFLUZA) REMAINING_____ CONFIRM STUDY MEDICATIONS REMAINING WILL BE MAILED IN STAMPED ENVELOPE PROVIDED AT ENROLLMENT _____

RESULTS OF PREGNANCY TESTING IN women of childbearing potential: POSITIVE_____**NEGATIVE**____

ONCE MEDICATION RETURNED RECORD: ELDERBERRY EXTRACT OR PLACEBO REMAINING IN ML_____ OSELTAMIVIR OR BALOXAVIR MARBOXIL PILLS ____ OR ML____ REMAINING

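### Section 8.7 ends follow-up of a pregnancy at symptom resolution, but the only scheduled post-baseline pregnancy test usually comes after that point, so no planned contact would obtain the pregnancy's outcome

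*Combined protocol and SAP*

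**What the plan says.** Testing. Section 6.2: "All women of childbearing potential will have a urine pregnancy test before starting and upon completion of the study". Section 6.3 repeats that "women of childbearing potential will have an end of study urine pregnancy test to be arranged at a nearby Cleveland Clinic Laboratory", and the Study Assessments table marks the test at baseline and at the final visit only, not on the daily calls.

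End of study. Section 3.2: "Patients will be followed daily until all symptoms have completely resolved and fever has remained less than 100° F for 24 hours". A patient who has not reached that state by day 21 completes then, with symptoms still present. Section 5.5 gives the same two end points for the daily calls, whichever comes first.

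Last-day form (attachment 14.2). The block that opens "ON LAST DAY OF STUDY CONFIRM ALL SYMPTOMS RESOLVED AND TEMPERATURE" also holds the pregnancy result, as positive or negative only.

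What follows a pregnancy. Section 8.7, in a sentence shared with allergy to study medication: patients who "become pregnant during the study they will be withdrawn from the study with ongoing follow-up until their acute symptoms resolve". Section 4.4.2 limits data collection on withdrawn subjects to the time until they are well, or 21 days, and only if they accept the calls.

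Serious events. Section 8.1 lists "a congenital anomaly/birth defect" among the outcomes that make an event serious. Section 8.2 requires a serious event arising after the study period to be recorded and reported if it is thought possibly related.

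**The concern.** The protocol treats pregnancy as a risk to be controlled. It excludes pregnant women, requires contraception, tests twice and counts a birth defect as a serious adverse event. The 8.7 rule that should act on a positive test uses a stopping point that makes sense for an allergic reaction but has no bearing on a pregnancy. If that point has already passed when the test is taken, the test produces a result on which the plan takes no further step. At stake is safety capture: whether the trial would ever learn how an exposed pregnancy ended.

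**Working it through.** This is a check of sequence; there is no stated figure to reproduce and no statistical formula applies.

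Let R be the time when all symptoms have completely resolved, C the end of participation and T the time of the final pregnancy test.

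- From 3.2 and 5.5: C = R + 24 hours if that falls within 21 days of enrollment; otherwise C = day 21.
- From 6.2 and 6.3: T is at or after C. The test is arranged at an outpatient laboratory, and no interval between C and T is given.
- From 8.7: follow-up of a pregnancy ends when acute symptoms resolve. The term is not defined. Its latest natural reading is R.
- Planned follow-up after a positive final test under 8.7 is therefore max(0, R − T).

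**Case 1, completion by recovery.** T ≥ R + 24 hours, so R − T ≤ −24 hours and follow-up is 0. The stopping condition was met at least a day before the test. Section 4.4.2 adds nothing, because she is already well. Withdrawal has no effect, because her participation is over.

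**Case 2, completion at day 21 with symptoms present.** Here R can fall after T, so 8.7 gives some follow-up, but only until symptoms resolve. Section 4.4.2, read on its own, stops at 21 days.

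**Case 3, pregnancy reported on a daily call before completion.** The withdrawal rule works as intended. Follow-up runs to symptom resolution under 8.7, and to recovery or at most 21 days under 4.4.2.

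In none of the three cases does planned contact extend to the outcome of the pregnancy.

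I then looked for another section that would supply it:

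- 6.2 attaches one consequence to a result, its disclosure to a minor subject and her parents or guardian.
- 8.2, 8.3 and 8.3.1 do not name pregnancy as something to record or report.
- The last-day form has no field for outcome or later contact.
- 8.2 covers possibly related serious events after the study period, but it acts only on events that become known to the study.

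**Timing against dosing.** Section 5.2 sets 5 days of dosing. No minimum interval separates the first or last dose from the final test. Completion by recovery has no earliest day, so a test before day 5 is not ruled out. At the other extreme, completion at day 21 falls about 21 − 5 = 16 days after dosing ends. The interval from exposure to test thus depends on how fast the patient recovers, and the protocol does not say what the test is meant to detect.

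**The case against.** The strongest objection is that a reporting route exists. A reader might infer that a birth defect could not be captured at all. The documents do not support that: 8.2 requires a possibly related serious event after the study period to be recorded and reported immediately, and 8.3.2 deals with events later found reportable. This objection stands. What it leaves untouched is that the route is passive, since nobody is scheduled to ask.

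A second objection also stands: the test does not always follow resolution. Case 2 is a real exception, and in Case 3 the pregnancy is known before the final test. The claim has to be limited to the usual sequence.

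Third, a reader might infer that an early final test misses every conception during dosing, or that an effective supplement would bring earlier testing, and so poorer detection, in the active arm. Neither can be shown here. The documents give no detection window for a urine test and no distribution of recovery times. Pregnancy is not an endpoint or a planned comparison between arms. What remains is only that the timing follows recovery and has no stated link to dosing.

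Fourth, the number of women concerned is small. The trial enrolls 65 to 100 patients of both sexes from age 5 upward, doses for 5 days, tests at baseline and requires contraception. This limits the importance of the point but does not answer it.

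Finally, the consent pages were not available, nor was the text of attachments 14.3 and 14.4, which the contents list names. They may contain pregnancy instructions. If so, sections 4.4.2 and 8.7 would still need to agree with them.

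**Conclusion.** The point holds in limited form. For a woman who completes by recovery, planned follow-up after a positive final test is zero under 8.7 and 4.4.2. For any pregnancy, however found, no planned contact reaches its outcome. A congenital anomaly would be captured only through a spontaneous report under 8.2.

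This is a stated rule that does not serve the protocol's own safeguards, so it goes beyond missing detail. The conclusion assumes that acute symptoms in 8.7 means the influenza symptoms or other acute complaints, not the pregnancy itself, and it covers the available text only. The documents do not give the number of women of childbearing potential, so the number affected cannot be calculated; it is likely to be few. The primary analysis, secondary analyses and sample size are not affected. The sponsor should make the change, but it does not bear on the trial's efficacy conclusions.

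**What to change.** - **8.7:** take pregnancy out of the sentence tied to acute symptoms. State that any pregnancy found during the study or at the final test is recorded and reported, and that its outcome is obtained by phone or chart review.
- **4.4.2:** make the limit of recovery or 21 days consistent with this.
- **6.2, 6.3 and the Study Assessments table:** say what follows a positive final test.
- **8.1 and 8.2:** cross-refer, so that the listed birth-defect outcome has a planned source of information.
- **14.2:** add a place to record that a pregnancy was reported and how it ended.
- **Test timing:** the sponsor should state the purpose of the end-of-study test and reconcile its timing with that purpose and with the 5-day dosing period. No particular test day is proposed here.

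The cost is protocol wording, a change to the consent wording so that contact after recovery is agreed in advance, and a few phone calls or chart checks if a pregnancy occurs. None of the items above adds a laboratory test or changes the analysis.
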